## RESEARCH STRATEGY

### **1. Significance**

Both opportunities and challenges exist for smoking cessation during pregnancy and postpartum. High motivation to quit during pregnancy is often followed by high chance of relapse during postpartum. About 23% of U.S. women smoke before pregnancy, and 54% of them report quitting smoking during pregnancy. But most of women who quit smoking during pregnancy return to smoking ("relapse") after delivery, e.g., 45%, 70%, and 81% relapse by 6, 9, and 12 months postpartum, respectively. Postpartum smoking relapse not only limits the benefits of smoking abstinence to the mother, but also has serious negative consequences for child health and development via tobacco metabolites in breast milk and ambient air. Child risks include fast infancy weight gain and childhood overweight as shown in our studies, infant respiratory illness such as asthma, and sudden infant death syndrome. Preventing postpartum smoking relapse remains a challenge for research and clinical practice. According to a recent review of 32 relevant studies, few existing pharmacological, behavioral, and contingent incentive-based interventions have been proven to be effective on preventing smoking relapse in long-term postpartum period (e.g., 9 months or longer), although several incentive-based studies were still effective up to 6 months postpartum (longer assessment unavailable). Indeed, in a large trial published recently, the intervention focusing on ex-smoking mothers' concerns about mood, stress, and weight did not improve smoking abstinence at 12 months postpartum. Novel and effective interventions are urgently needed to address the large public health issue of postpartum smoking relapse.

Numerous stressors in postpartum life and negative affect such as depression, anxiety, anger, and fear are reported as common triggers for postpartum smoking relapse. Interestingly, breastfeeding mothers tend to have lower perceived stress and less negative affect including depression and anger, than formula-feeding mothers. While the directions of these associations are difficult to determine from observational studies, in a within-subject design study, maternal negative affect decreased after a breastfeeding episode in the same mothers, whereas maternal positive affect decreased after a formula-feeding episode. In addition, early termination of breastfeeding is associated with increased depression and anxiety. These breastfeeding-related emotional benefits may be attributed to unique neuroendocrine changes to maintain breastfeeding, especially higher oxytocin and prolactin levels. These neuroendocrine and psychological mechanisms may explain our and others' observation that smoking relapse is much less common (30-60% lower risk) among breastfeeding mothers than formula-feeding mothers. Therefore, it is reasonable to hypothesize that a breastfeeding promotion intervention can reduce the risk of postpartum smoking relapse through increased oxytocin and prolactin while decreased maternal stress and negative affect. Our application is the first randomized controlled trial to test this promising hypothesis.

In a pilot survey ([name] as PI), we found poor breastfeeding knowledge among 21 pregnant and 18 postpartum women who quit smoking during pregnancy. Only 28.6% agreed "Babies should be exclusively breastfed for the first 6 months (current clinical guidelines)", 52.4% agreed "The best way to feed a baby is breastfeeding", and 38.1% agreed "If a baby is breastfed he or she will be less likely to get diarrhea". Their intention to breastfeed was also relatively low: only 42.9% planned to breastfeed exclusively in the first weeks after delivery, and only 9.5% planned to exclusively breastfeed for 6 months. Their actual breastfeeding practice was even lower: only 22.2% and 0% breastfed exclusively in the first week and 6 months after delivery, respectively. Quitters tend to wean their infants sooner than nonsmokers, and their breastfeeding rate at 4 months postpartum is similar to that of continuous smokers'. These consistent data suggest an urgent need to promote breastfeeding among women who quit smoking during pregnancy. One of our key team members, [name] (Co-I), has developed, tested, and published a highly effective intervention funded by NIH to increase breastfeeding duration among low income mothers. For instance, the breastfeeding rate at 6 months postpartum was 72% in the intervention group, compared to 0% in the usual care group. We plan to modify her intervention to promote breastfeeding among ex-smoking mothers in the proposed project.

**Conceptual model (Figure 1).** Through suckling stimuli and intimate mother-infant contact (e.g., infant hand massage and skin-to-skin contact, breastfeeding promotes the release of two key lactation hormones from the pituitary gland: prolactin (hormone for milk synthesis) and oxytocin (hormone for milk ejection)). Both oxytocin and prolactin can reduce maternal stress response through dampening hypothalamic-pituitary-adrenal (HPA) activity, which can lead to lower and/or fewer surges of adrenocorticotrophic hormone (ACTH) and cortisol. Oxytocin and possibly prolactin also decrease maternal negative affect through reducing amygdala activation. In addition, breastfeeding helps to enhance mother-infant bonding, possibly through the activities of oxytocin in brain to decrease aggressive responses toward offspring. Intervention targeting mother-infant bonding can decrease postpartum smoking relapse up to 8 weeks postpartum, possibly because a strong mother-infant bond can foster positive mother-infant interaction. The positive

mother-infant interactions may serve as an alternative reward pathway that may decrease frequency and intensity of cravings for cigarettes. It could potentially shift the focus of ex-smoking breastfeeding mothers' dopamine reward system from smoking to caring for the child. As positive mother-infant interactions increase, the mother's investment (e.g., time, attention, money) in her child may increase, while her cravings for smoking are expected to diminish. The mother's process of replacing cravings for smoking with increasing investment in the child and building a positive caregiving relationship may be gradual but may also be sustainable over time, which is indirectly supported by previous research in which parenting intervention is associated with substance use reduction and pup suckling is more rewarding than cocaine in the immediate postpartum period. This natural alternative reward system (positive mother-infant interaction) along with low maternal stress and negative affect may help breastfeeding mothers to achieve long-term postpartum smoking abstinence.

**2. Innovation** Our proposed project is innovative in several ways. First, it is the first randomized

controlled trial to assess the effect of breastfeeding promotion on postpartum smoking relapse. It can help to yield causal evidence by overcoming self-selection bias and confounding (e.g., health motivation, socio-economic status [SES], partner and family support) in previous observational research. Secondly, we will collect pilot data to examine neuroendocrine (oxytocin and prolactin), behavioral (mother-infant interaction), and psychological (mother-infant bonding, stress, and negative affect) mechanisms through which breastfeeding may reduce risk of postpartum smoking relapse. Thirdly, this is a pioneering study to combine contingent incentives with other intervention strategies such as education, counseling, support, and early limited formula milk via syringe to further improve breastfeeding practice among disadvantaged mothers.

[figure not shown]
### **3. Approach**

**3.1 Research Design.** **3.1.1 Overview.** This is a randomized controlled trial to prevent postpartum smoking relapse by breastfeeding promotion. The intervention group (N=30) will receive multicomponent breastfeeding intervention from late pregnancy to 6 months postpartum, while the usual care control group (N=30) will only receive minimum breastfeeding education. The key outcome is the timing of postpartum smoking relapse.

**3.1.2 Recruitment.** We will recruit 60 pregnant ex-smokers from Erie County and Niagara County, NY. Recruitment flyers will be distributed around the communities (e.g., churches, bus/subway stops, laundromats, grocery stores, thrift stores, community centers) and organizations providing basic services (e.g., social services, WIC, job training) to low income pregnant women. Recruitment flyers will also be displayed in 4 large city OB/GYN clinics. Health professionals at these clinics will pass our recruitment materials to ex-smoking patients. We will also send an invitation letter to potentially eligible pregnant women in these clinics. The PI has successful experience in recruiting 50 pregnant smokers for his NIH funded study on smoking cessation during pregnancy over 6 months from 2 obstetric clinics (see **Letters of Support** from clinics). Social media such as Facebook will also be used. Assuming a rate of 23% maternal smoking at conception and 54% smoking cessation rate during pregnancy, we estimate 1,490 out of about 12,000 newborns will be born to mothers who quit smoking during pregnancy within 1 year in the two counties. We assume 60% of these mothers (N=894) will be exposed to recruitment materials, and then 30% (N=268) are interested in this project. Therefore, it is feasible to recruit 72 (60 + 20% attrition) eligible participants within 1 year.

**3.1.3 Screening.** Interested participants will sign consent forms and complete a survey on socio-demographics, pregnancy, medical history, mental health, history and status of cigarette smoking, use of other tobacco or nicotine products, alcohol and other substance use, and infant feeding plan. Those who had quit smoking cigarettes within 3 months before or during this pregnancy will be invited for lab screening to verify their current non-smoking status by urine cotinine (metabolite of nicotine). Collateral reports (e.g., from employer, partner, friend, or relative) or medical records will be used to verify their previous smoking history. Eligible participants

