**Figure 1. Conceptual Model for Breastfeeding and Smoking Abstinence\***

\* Other hormonal mechanisms, such as progesterone, estrogen, ACTH, cortisol, and tetraiodothyronine (T4), will be included in the larger R01 grant.

must be at 28 weeks of pregnancy or earlier to ensure adequate time for prenatal breastfeeding intervention. Exclusion criteria are teen pregnancy (<18 y); current use of other tobacco or nicotine products; medical conditions contraindicating breastfeeding such as HIV infection, active tuberculosis, and breast removal; current heavy drinking (more than 2 drinks a day); current use of other psychoactive substances; being strongly against breastfeeding; and non-English speakers. To increase the possibility to obtain a representative sample of the generable population, the study will be advertised as a program to promote healthy infant feeding among pregnant women without requiring breastfeeding intention or mentioning smoking relapse prevention. We will not exclude women without current intention to breastfeed (28.6% in our pilot survey), unless they are strongly against breastfeeding (4.8%). Similarly, we will not exclude women who plan to relapse after delivery (0% in our pilot survey), as our breastfeeding promotion may motivate them to maintain abstinent for a longer period especially if they know tobacco metabolites are concentrated in breast milk.

**3.1.4 Pre-test visit.** During this visit, we will measure the participant's urine cotinine, height, and body weight. Participants will complete a survey on smoking temptations, nicotine dependence before quitting, smoking cessation history, self-efficacy to maintain smoking abstinence, smoking environment including partner smoking behaviors, breast health, breastfeeding knowledge, breastfeeding history, relationship with partner and other family members, social network, stress, negative affect, physical activity, sleep, and diet.

**3.1.5 Randomization.** At 28 weeks of pregnancy, eligible participants will be randomized into either the intervention group (N=30) or the control group (N=30) using a sequence of random numbers in blocks of 2, which can ensure equal or close numbers of participants between the two groups throughout the project.

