**Timing of maternal postpartum smoking relapse.** The participant will use a calendar to record the daily number of cigarettes smoked, if any, throughout the study period. Based on SRNT guidelines, the date of postpartum relapse will be defined as the first day after delivery on which an ex-smoker has smoked for 7 consecutive days, or has smoked at least once each week over 2 consecutive weeks. Similar definitions were used in previous studies on postpartum smoking relapse. The self-reported smoking abstinence will be biochemically confirmed by urine cotinine tests with HPLC-MS/MS assay performed by an outside laboratory (Kaleida Health Lab, Buffalo, NY). As recommended by SRNT, a cut-off point of 50 ng/mL urine cotinine will be used to define current smoking. There is a possibility that some participants may relapse during pregnancy (*prenatal* smoking relapse). If the relapse happens before randomization, they will be removed from this study. Otherwise, they will continue to receive breastfeeding intervention and be included in intent-to-treat analysis.

**Breastfeeding duration.** We will measure the initiation, duration, and exclusivity of breastfeeding by interviewing the mother at each postpartum visit using a questionnaire modified from 2 US national birth cohorts. Postpartum mothers will report their current feeding method, frequency, and duration of breastfeeding and/or formula use. Breastfeeding status will be visually verified by a female research staff,

looking for one of the following indicators of successful breastfeeding in the infant – audible swallowing, a regular suck/swallow/breath pattern, or visible milk in the infant's mouth after they are not latched anymore. For a mother who pumps milk, staff will observe pumping combined with the resulting milk being fed to the infant. This visual verification of breastfeeding/pumping was acceptable to participants in [name] study.

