*Maternal negative affect.* Maternal negative affect will be measured at enrollment and all postpartum visits using the Positive and Negative Affect Schedule (PANAS). The 10 items on negative affect include being distressed, upset, guilty, ashamed, hostile, irritable, nervous, jittery, scared, and afraid. Participants will rate their experience of each particular emotion in the past few weeks. With this time frame, its Cronbach's alpha was 0.87 and test-retest reliability was 0.48. In addition, we will measure maternal anxiety with the State-Trait Anxiety Inventory and postpartum depression with the Edinburgh Postnatal Depression Scale.

**3.1.10 Covariates.** We consider partner smoking, maternal secondhand smoke exposure, education, household income, health motivation, perceived social support, as covariates. They may confound our results and will be controlled in data analysis if not comparable between intervention and control groups.

**3.1.11 Economic costs.** We will collect information on intervention (not research and development) costs such as personnel, recruitment, materials, compensation, incentives, and transportation. We will include outcome costs for formula, medical care of NICU stay and sick child visits, and parental absenteeism for infant illness.

**3.1.12 Statistical Analysis.** *Specific Aim 1 (Breastfeeding promotion and postpartum smoking relapse).* The timing of postpartum smoking relapse (outcome) will be analyzed with Cox regression model by including group assignment (intervention vs control), smoking status (1=smoking, 0=non-smoking), the observed time, and significant covariates. The proportional hazard ratio of postpartum smoking relapse between two groups will be calculated. We will estimate Kaplan-Meier survival curves to visually compare smoking trajectories. Intent-to-treat analysis will be used with all randomized participants being included in their originally assigned groups. Dropouts, losses to follow-up, fetal deaths, and miscarriages will be coded as missing data on smoking status. If missing data on smoking status is more than 20%, we will run pattern mixture models and sensitivity analyses. A supplemental analysis will be run to examine *prenatal* smoking relapse during pregnancy.

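### Pre-quit nicotine dependence and time since quitting have no guaranteed place in the Aim 1 Cox model, because covariates are chosen by data-driven rules

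*Combined protocol and SAP*

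**What the plan says.** **Entry (3.1.3).** "Those who had quit smoking cigarettes within 3 months before or during this pregnancy will be invited for lab screening". Eligible women "must be at 28 weeks of pregnancy or earlier to ensure adequate time for prenatal breastfeeding intervention". Urine cotinine confirms that a woman is not smoking at screening; no minimum length of abstinence is set.

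**Randomisation (3.1.5).** Women are allocated at 28 weeks "using a sequence of random numbers in blocks of 2, which can ensure equal or close numbers of participants between the two groups". No stratification factor is named. On relapse between entry and allocation, 3.1.8 says: "If the relapse happens before randomization, they will be removed from this study".

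**Baseline data (3.1.3 and 3.1.4).** The screening survey covers smoking history and status. The pre-test survey includes "nicotine dependence before quitting, smoking cessation history, self-efficacy to maintain smoking abstinence".

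**Covariates (3.1.10).** Six are listed: partner smoking, secondhand smoke exposure, education, household income, health motivation and perceived social support. The rule is: "They may confound our results and will be controlled in data analysis if not comparable between intervention and control groups".

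**Primary model (3.1.12).** A Cox model for time to postpartum relapse with group assignment and those covariates that are significant. The section does not say which candidates are considered, or significant in what test.

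**The concern.** The primary outcome is time to smoking relapse. How dependent a woman was before quitting, and how long she has been abstinent, are natural candidates for predicting it. The sponsor measures the first directly and holds the history from which the second can be derived, but the analysis assigns neither a role.

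The two inclusion rules also differ. Section 3.1.10 looks at balance between arms; 3.1.12 looks at significance. Both are applied after the data are seen, and neither fixes the set of candidate variables. Different analysts could reach different adjusted hazard ratios from the same 60 women, all within the plan.

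With 30 per arm, chance differences in underlying relapse risk can be sizeable, and the trial has little power to spare. Prognostic information that is already held should be used in a way fixed in advance.

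**Working it through.** **1. The plan's own figures.** Section 3.1.13 gives 98 per group (45% vs 25% at 6 months) and 46 per group (70% vs 39% at 9 months). For the 9-month rates, with two-sided alpha 0.05 and power 0.80:

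- Uncorrected: n = [1.96√(2 × 0.545 × 0.455) + 0.842√(0.70 × 0.30 + 0.39 × 0.61)]² / 0.31² = 39.3.
- Continuity-corrected: (39.3/4) × [1 + √(1 + 4/(39.3 × 0.31))]² = 45.5, so 46.

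The same formula gives 98 for the 6-month rates. Both figures reproduce, and both exceed the 30 per group planned.

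**2. Range of abstinence.** 28 weeks × 7 / 30.44 = 6.4 months. Adding the 3 months before pregnancy gives a maximum of 9.4 months at randomisation. There is no stated minimum. The outcome clock starts at delivery, about 12 weeks (2.8 months) later if birth is at 40 weeks (an assumption). A woman still abstinent then has therefore been so for between about 2.8 and 12.2 months.

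**3. Chance imbalance.** Take a binary factor with 50% prevalence and independent Binomial(30, 0.5) counts in each arm. A 20-point gap is 6 women, and P(difference of 6 or more) = 0.155. At 30% prevalence it is 0.120.

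**4. Value of adjustment.** The documents give no hazard multiple for either variable, so the multiples below are assumptions. The simulation used 30 per arm, exponential times, censoring at 9 months, no dropout, one binary factor at 50% prevalence and 5,000 trials per row. Both arms were calibrated to the plan's 70% and 39%.

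| Assumed multiple | Power unadjusted | Power adjusted | Gain (points) | Mean HR unadjusted | Mean HR adjusted |
|---|---|---|---|---|---|
| 1.5 | 69.0% | 69.9% | 0.9 | 0.41 | 0.40 |
| 2 | 68.9% | 72.4% | 3.5 | 0.41 | 0.39 |
| 3 | 71.2% | 80.0% | 8.8 | 0.40 | 0.36 |
| 4 | 72.0% | 84.9% | 12.9 | 0.39 | 0.33 |

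A second set-up fixes the conditional hazard ratio at ln(0.61)/ln(0.30) = 0.41. With 1,000 trials per row at multiples of 2, 3 and 4, power is 69% vs 71%, 63% vs 71% and 61% vs 74%, gains of 2, 8 and 13 points. With 5,000 trials the gains are 2.7, 9.2 and 14.6. In this set-up the intervention arm relapses at 40%, 42% and 44%, so it no longer matches the plan's 39%.

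**5. Room in the model.** Expected events by 9 months before attrition: 30 × 0.70 + 30 × 0.39 = 32.7. Treatment plus two covariates is three terms, or 32.7/3 = 10.9 events per term. If the expected 20% attrition removed events in proportion, 0.8 × 32.7 = 26.2 would remain, or 8.7 per term.

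**The case against.** The strongest reply is that nothing here is biased. Randomisation balances both variables in expectation, and the test's error rate already allows for chance imbalance. The trial is a 60-woman pilot for a larger project, no document says how strongly either variable predicts relapse, and the gain at a multiple of 1.5 is about one point. All of that stands, and it limits the point to precision and prespecification.

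Four stronger readings are tempting, and the documents do not support them.

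- **The two variables can never enter the model.** The undefined significance clause in 3.1.12 is not expressly confined to the 3.1.10 list, so it might admit them. They are unnamed and not guaranteed, which is a weaker statement.
- **The unadjusted hazard ratio is wrong, pulled toward 1.** The drift appears only if 0.41, which comes from the marginal rates of 70% and 39%, is treated as a conditional hazard ratio. With both arms calibrated to those rates, the unadjusted value stays near 0.39 to 0.41. Marginal and conditional hazard ratios differ in a Cox model, and neither is an error.
- **The trial compares women abstinent for days with women abstinent for nine months.** Very short abstinence is only what the criteria permit, not a described subgroup. Women who relapse before randomisation are removed, and the outcome clock starts at delivery.
- **Both variables are named pre-test items.** Only dependence is. Time since quitting has to be derived from the smoking history.

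What the reply does not answer is that two differing data-driven rules decide the primary model.

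**Conclusion.** The point holds as a matter of precision and prespecification. The plan admits women with widely varying abstinence and collects the relevant history, but does not commit to using it in the Aim 1 model. Its covariate rules depend on observed balance and on an undefined test of significance.

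For one binary factor at 50% prevalence with an assumed hazard multiple of 2 to 4, adjustment is worth about 2 to 13 points of power before dropout, give or take a point or two between runs and set-ups. A weak factor would gain almost nothing. The 15.5% chance of a 20-point imbalance rests only on 30 per arm and 50% prevalence. The simulation covers one covariate, while the change below adds two, so it illustrates the size of the gain and does not forecast it.

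A reader might infer that the entry window is too broad or that stratified randomisation is required. Neither follows: adjustment uses the same information without narrowing the population or changing the allocation.

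**What to change.** In 3.1.10 and 3.1.12, state that the Aim 1 Cox model always includes group, pre-quit nicotine dependence and time since quitting at randomisation, regardless of observed balance or significance. Derive time since quitting from the quit date needed to apply the screening rule, and confirm that the screening form records that date. State the form of each variable (for example, continuous and linear) so that each uses one degree of freedom.

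Replace both the comparability trigger and the significance trigger with this fixed set. If the six listed covariates are still wanted, place them in a labelled sensitivity analysis: with group and the two new variables they would make nine terms, or 32.7/9 = 3.6 expected events per term.

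Report the unadjusted hazard ratio alongside, noting that the adjusted one is conditional and the two need not coincide.

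The cost is analysis-plan wording and two degrees of freedom against about 33 expected events before attrition. No new visits are needed, and no new data provided the quit date is captured. Eligibility and randomisation do not change.
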